9.8 Changes in the Conduct of the Study or Planned Analyses

9.8.1 Changes in the Conduct of the Study

The original protocol, dated 09 March 2016, was amended 3 times. A copy of the final study protocol (Protocol PHN-Udenafil-02, dated 31 August 2017) is provided in [Appendix 16.1.1](#).

Version 2 of the protocol (04 May 2016) included the following substantive modifications to the original protocol:

- Added a DSMB review of all data after the first 50 subjects had completed the study.
- Added the opportunity for subjects to enroll in a heart rhythm-monitoring subset of the FUEL study.

Version 3 of the protocol (30 May 2017) included the following substantive modifications to Version 2 of the protocol:

- Conversion of Visits 2 and 3 to telephone calls, removing vital sign measurements.

Version 4 of the protocol (31 August 2017) included the following substantive modifications to Version 3 of the protocol:

- Addition of inclusion criterion #4, which required potential participants to be on anti-platelet or anticoagulant therapy.
- Addition of exclusion criterion #26, which excluded potential participants if they had a history of clinically significant thromboembolic event.

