9.8.2.2 Changes Between Finalization of Statistical Analysis Plan and Blind Break

Key changes to statistical analyses between SAP finalization on 23 June 2016 and blind break on 19 July 2019 are described below.

Treatment group differences for the primary efficacy endpoint were summarized descriptively for subjects on afterload reducing agents in the study versus subjects who were not on afterload reducing agents in the study.

Analyses by visit were updated to account for protocol version 3, which replaced in-person Visits 2 and 3 (at Weeks 2 and 13, respectively) by telephone calls, and to remove collection of vital sign measurements at those time points.

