12.5 Vital Signs, Physical Findings and other Observations Related to Safety

Mean changes from baseline in blood pressure and heart rate were small and generally similar between treatment groups ([Table 41](#)). Statistically significant treatment group differences were observed for change in diastolic blood pressure from baseline to Week 2 and to Week 26, with greater decreases in the udenafil group.

Table 41: Changes in Blood Pressure and Heart Rate from Baseline to Week 2, Week 13, and Week 26 (Safety Population)

	Udenafil (N=200)	Placebo (N=200)	p-value^a
Systolic blood pressure (mmHg)			
Baseline ^b	n=200	n=200	
Mean (standard deviation)	112.32 (12.136)	113.21 (12.887)	0.477
Week 2 – baseline ^c	n=154	n=155	
Mean (standard deviation)	-1.34 (14.846)	-0.64 (15.424)	0.682
Week 13 – baseline ^c	n=131	n=143	
Mean (standard deviation)	-1.15 (13.000)	-1.26 (13.978)	0.948
Week 26 – baseline	n=189	n=190	
Mean (standard deviation)	-1.90 (12.166)	-0.49 (11.535)	0.246
Diastolic blood pressure (mmHg)			
Baseline ^b	n=200	n=200	
Mean (standard deviation)	68.39 (9.508)	69.30 (10.142)	0.355
Week 2 – baseline ^c	n=154	n=154	
Mean (standard deviation)	-4.34 (12.113)	-1.46 (12.398)	0.040
Week 13 – baseline ^c	n=131	n=143	
Mean (standard deviation)	-3.75 (11.374)	-1.95 (12.695)	0.220
Week 26 – baseline	n=189	n=190	
Mean (standard deviation)	-3.01 (9.644)	0.05 (10.696)	0.004
Heart rate (bpm)			
Baseline ^b	n=200	n=200	
Mean (standard deviation)	87.52 (15.253)	88.12 (14.128)	0.683
Week 2 – baseline ^c	n=154	n=155	
Mean (standard deviation)	-6.90 (13.464)	-8.30 (14.810)	0.385
Week 13 – baseline ^c	n=131	n=143	
Mean (standard deviation)	-6.94 (15.606)	-7.83 (14.230)	0.621
Week 26 – baseline	n=189	n=190	
Mean (standard deviation)	-1.06 (12.725)	-1.02 (12.448)	0.977

a P-value was assessed using analysis of variance with fixed factor for treatment group.

b Last pre-drug administration measurement.

c Collection of blood pressure and heart rate at Week 2 and Week 13 was stopped in the middle of the study and removed from the protocol version 3.0 (31 August 2017).

Source: [Table 14.3.23](#)

Program: [T_14_3_23.sas](#)

The percentages of subjects with potentially clinically significant vital sign values pre-6-minute walk and post-6-minute walk on Day 1 were small and similar between treatment groups. Potentially clinically significant vital sign changes on Day 1 are

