2.0 Overall Study Design

This study is a randomized, double-blind, 26-week, multicenter trial of udenafil (87.5 mg, twice daily) versus placebo on aerobic exercise performance as measured by change in minute oxygen consumption (VO₂) at maximum exercise effort (maximal VO₂) from baseline to six months in adolescent survivors of the Fontan procedure.

Eligible subjects will be randomly assigned to one of two treatment groups (udenafil or placebo) by a web-based system at the data coordinating center. Randomization will occur within strata defined by ventricular morphology (single left versus single right or mixed).

The first dose of randomized study drug will be administered at the clinic (Visit 1) and outpatient dosing will be used for the remainder of the 26-week study. Subjects will return to the clinic for assessments at 2 weeks (Visit 2), 13 weeks (Visit 3), and 26 weeks (Visit 4) or study completion after initiation of study drug dosing.

Maximal VO₂ will be assessed at Visits 1 and 4 (or study completion) using a braked cycle ergometer following a ramp protocol. Additional assessments will include ventricular performance as measured by echocardiogram, endothelial function assessment with EndoPat®, and serum brain-type natriuretic peptide (BNP) level. Quality of life will be assessed with the Pediatric Quality of Life Inventory (PedsQL), Pediatric Cardiac Quality of Life Inventory (PCQLI), and the Habitual Activity Estimation Scale (HAES).

Blood samples for pharmacokinetic assessments of udenafil and its primary metabolite will be obtained after the first dose of randomized study drug and at Visit 4 (or study completion). Safety will be monitored by adverse event reports, resting vital signs, and clinical laboratory tests.

When an individual subject completes the study, the subject's primary cardiologist will be notified, and the study drug will be stopped; there will be no need to wean subjects off the study drug. Subjects will not be told which drug they received until all recruitment and follow-up is completed per-protocol. All subjects will be invited to participate in an open-label, 12-month safety extension trial of udenafil.

CONFIDENTIAL

The blind for the study will be broken when the later of the following 2 events occur and all database queries have been resolved:

- Visit 4 is completed for the last subject who enters the safety extension trial, or

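### Table 41 tests vital signs visit by visit without baseline adjustment, on incomplete Week 2 and Week 13 readings, so the diastolic result is less precise than it could be and is described by significance, not size

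*Protocol*

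**What the plan says.** SAP 2.0 planned all three post-baseline visits in person: "Subjects will return to the clinic for assessments at 2 weeks (Visit 2), 13 weeks (Visit 3), and 26 weeks (Visit 4"). SAP 6.5.4 planned a descriptive summary of change from baseline at each scheduled assessment, and SAP 6.5 planned no formal hypothesis testing for safety.

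Protocol 9.8.1 lists the version 3 change as "Conversion of Visits 2 and 3 to telephone calls, removing vital sign measurements". Protocol 9.8.2.2 records, among changes made before the blind was broken, "Analyses by visit were updated to account for protocol version 3", and adds that this was also "to remove collection of vital sign measurements at those time points".

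Table 41 gives change from baseline at Weeks 2, 13 and 26, each row on whoever had a reading. Its footnote c discloses the stop: "Collection of blood pressure and heart rate at Week 2 and Week 13 was stopped in the middle of the study". Its p-values come from an ANOVA with treatment as the only factor, run separately at each visit. The text opens: "Mean changes from baseline in blood pressure and heart rate were small and generally similar between treatment groups". It then names significant diastolic differences at Weeks 2 and 26, with larger falls on udenafil. Section 12.6 concludes that there were no clinically important differences between arms in vital signs.

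**The concern.** Blood pressure and heart rate are central safety measures for a vasodilator. Two features of Table 41 make its between-arm evidence weaker than the data allow.

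- The ANOVA of change ignores the baseline value and uses each visit alone. Regression to the mean stays in the error term, and nothing is borrowed from a subject's other visits. This costs most at Weeks 2 and 13, where a quarter to a third of readings are absent.
- The result is told through p-values. Naming Weeks 2 and 26 and omitting Week 13 suggests a diastolic effect that comes, goes and returns, when Week 13 simply has the fewest subjects and the widest interval.

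Separately, small is a poor description of the heart-rate rows at Weeks 2 and 13, and the document gives two dates for the version that ended collection.

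**Working it through.** **1. Coverage (n from Table 41, 200 per arm; diastolic at Week 2 has 154 on placebo)**

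| Visit | Udenafil | Placebo | Total |
|---|---|---|---|
| Week 2 | 154 (77.0%) | 155 (77.5%) | 309/400 = 77% |
| Week 13 | 131 (65.5%) | 143 (71.5%) | 274/400 = 69% |
| Week 26 | 189 (94.5%) | 190 (95.0%) | 379/400 = 95% |

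Week 13 coverage does not clearly differ by arm (Fisher p = 0.24). The least possible overlap with Week 26 is n(early) + n(26) - 200 per arm. That gives 143/154 and 145/155 for Week 2, and 120/131 and 133/143 for Week 13: about 92% or more.

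**2. Reproducing the printed diastolic p-values**

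With two arms, one-factor ANOVA is the pooled t-test: SE = s_p × √(1/n₁ + 1/n₂) and t = difference/SE. At Week 13, s_p = √[(130 × 11.374² + 142 × 12.695²)/272] = 12.08, SE = 12.08 × √(1/131 + 1/143) = 1.46, and t = -1.80/1.46 = -1.23.

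| Visit | Difference (mmHg) | SE | 95% CI | p, recomputed | p, printed |
|---|---|---|---|---|---|
| Week 2 | -4.34 - (-1.46) = -2.88 | 1.40 | -5.63 to -0.13 | 0.040 | 0.040 |
| Week 13 | -3.75 - (-1.95) = -1.80 | 1.46 | -4.68 to 1.08 | 0.219 | 0.220 |
| Week 26 | -3.01 - 0.05 = -3.06 | 1.05 | -5.12 to -1.00 | 0.004 | 0.004 |

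The systolic and heart-rate p-values also reproduce within rounding.

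**3. Is Week 13 different?**

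Its interval contains both other estimates. Week 13 minus Week 26 is 1.26 mmHg. If the two estimates were independent, the SE of that gap would be √(1.46² + 1.05²) = 1.80. They share subjects, so some correlation is likely. Even at an assumed correlation of 0.8, the SE is √(1.46² + 1.05² - 2 × 0.8 × 1.46 × 1.05) = 0.88, and 1.26/0.88 = 1.4. There is no evidence of a lapse. The Week 13 SE is 1.46/1.05 = 1.39 times the Week 26 SE.

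**4. What baseline adjustment would gain**

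The pooled baseline SD is s₀ = √[(9.508² + 10.142²)/2] = 9.83. The pooled SDs of change, s_c, are 12.26, 12.08 and 10.18. The SD of the follow-up values is not printed. I assume it is k × s₀ with k from 0.9 to 1.15, and that the full-sample baseline SD applies to each visit's subjects. With s₁ = k × s₀, r = (s₀² + s₁² - s_c²)/(2 s₀ s₁), and the ratio of adjusted to unadjusted SE is s₁√(1 - r²)/s_c.

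| Visit | SE cut, k = 0.9 | k = 1.0 | k = 1.15 | Adjusted SE |
|---|---|---|---|---|
| Week 2 | 28.5% | 21.8% | 13.1% | 1.00 to 1.21 |
| Week 13 | 27.8% | 21.1% | 12.5% | 1.06 to 1.28 |
| Week 26 | 20.7% | 14.5% | 6.8% | 0.83 to 0.98 |

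Any further gain from using all visits jointly cannot be computed, because correlations between visits are not given.

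**5. Heart rate**

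Mean changes, udenafil/placebo, are -6.90/-8.30 at Week 2, -6.94/-7.83 at Week 13 and -1.06/-1.02 at Week 26. The n-weighted means are (154 × -6.90 + 155 × -8.30)/309 = -7.60, and likewise -7.40 and -1.04 bpm. All four early-visit 95% intervals lie below -4.2 bpm; both Week 26 intervals include zero. Between-arm differences are +1.40 (-1.77 to 4.57), +0.89 (-2.66 to 4.44) and -0.04 (-2.58 to 2.50).

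**6. Dates**

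Section 9.8.1 reads "Version 3 of the protocol (30 May 2017") and gives 31 August 2017 as the date of version 4. Footnote c reads "removed from the protocol version 3.0 (31 August 2017"). The two cannot both be right.

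**The case against.** The strongest defence is that Table 41 does what SAP 6.5.4 asked, prints every n, footnotes the stop, and compares randomised arms within each visit. A stop tied to the protocol version applies to both arms and does not by itself bias those comparisons. Safety was planned as descriptive, and a reader can derive the differences from the printed means and SDs. All of this stands. It limits the point to precision and wording. It does not justify selective reporting of significance in a section planned without hypothesis tests, and the adjusted estimates cannot be derived from the printed figures.

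A reader might infer more. The documents do not support these readings:

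- *That the rows describe different people.* At least about 92% of those measured at Weeks 2 and 13 also have Week 26 readings.
- *That the report presents a heart-rate fall on drug that wears off.* No passage describes such a course, and placebo shows the same pattern.
- *That exercise testing at baseline and Week 26, but not at Weeks 2 and 13, caused the heart-rate pattern.* The schedule is documented; the cause is conjecture.
- *That udenafil subjects were lost selectively before Week 13.* Subtracting one row's n from another's assumes that everyone measured at Week 13 was also measured at Week 2, which is not stated. The direct coverage comparison shows no clear difference.

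**Conclusion.** The point holds as one of efficiency and reporting. The between-arm comparisons are valid as they stand, but the diastolic estimates are less precise than they need be, and the significance statement makes compatible results look inconsistent. The size of the gain rests on the assumed follow-up SD and on using the full-sample baseline SD for the subsets. Whether the diastolic effect is sustained is for the joint model to show; the printed figures are compatible with that and show no lapse. The heart-rate description and the version 3 date need correcting whatever is decided about the model. Within-arm changes should not be read across visits, and the documents do not establish why they differ.

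**What to change.** 1. Fit one repeated-measures model to the Week 2, 13 and 26 values, with treatment-by-visit and baseline-by-visit terms. Report the between-arm difference with 95% CI at each visit and averaged over visits, labelled as an addition to the plan.
2. Describe the diastolic result in 12.5 from these estimates instead of listing the visits that reached significance.
3. For heart rate, replace small with the fall of 7 to 8 bpm seen in both arms at Weeks 2 and 13. Add that within-arm changes should not be compared across visits and that the cause is not established.
4. Reconcile the version 3 date in footnote c with section 9.8.1.

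The data are already held. The cost is one extra model in a section planned as descriptive, and a diastolic effect that may have to be stated as sustained, which is slightly less favourable to the drug. Items 3 and 4 are text edits.

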Incidence of potentially clinically significant changes from pre dose values in blood pressure and heart rate were tabulated at i) post first study dose but before the self-limited 6-minute walk, ii) after the 6-minute walk, and iii) at any time after dosing.

SUMMARY – CONCLUSIONS

EFFICACY RESULTS:

For the Udenafil-Udenafil group, change to Week 52 of FUEL Extension measures change in exercise capacity between 26 weeks and 78 weeks of udenafil treatment. This change represents persistence of initial effectiveness beyond 26 weeks. For the Placebo/De Novo-Udenafil group, change to Week 52 of FUEL Extension measures change in exercise capacity from pre-udenafil to after 52 weeks of udenafil treatment.

In the Placebo/De Novo-Udenafil group, mean exercise capacity and myocardial performance improved between pre-udenafil and after 52 weeks of udenafil treatment:

- Mean increase at peak exercise effort in VO₂ (58.00 mL/min), work rate (5.78 watts), and minute ventilation (2.41 L/min). When VO₂ was standardized by each subject's body weight, a mean decrease was observed (-0.93 mL/kg/min; 95% CI: -1.7 to -0.2 mL/kg/min).
- Mean increase in VO₂ at VAT of 12.90 mL/min (95% confidence interval [CI]: -23.1 to 48.9 mL/min). When standardized by each subject's body weight, a mean decrease was observed (-0.93 mL/kg/min; 95% CI: -1.5 to -0.4 mL/kg/min).
- Mean decrease in VE/VCO₂ at VAT of -0.77 (95% CI: -1.4 to -0.2).
- Mean increase in work rate at VAT of 0.58 watts (95% CI: -2.6 to 3.7 watts).
- Mean decrease in MPI of -0.04 (95% CI: -0.1 to 0.0).

In the Udenafil-Udenafil group, mean exercise capacity was improved while myocardial performance did not deteriorate between 26 weeks and 78 weeks of udenafil treatment:

- Mean increase at peak exercise effort in VO₂ (38.00 mL/min), work rate (2.99 watts), and minute ventilation (2.56 L/min). When VO₂ was standardized by each subject's body weight, a mean decrease was observed (-1.45 mL/kg/min; 95% CI: -2.3 to -0.6 mL/kg/min).
- Mean increase in VO₂ at VAT of 6.57 mL/min (95% CI: -47.9 to 61.0 mL/min). When standardized by each subject's body weight, a mean decrease was observed (-1.25 mL/kg/min; 95% CI: -2.1 to -0.4 mL/kg/min).
- Mean decrease in VE/VCO₂ at VAT of -0.66 (95% CI: -1.6 to 0.3).
- Mean increase in work rate at VAT of 0.26 watts (95% CI: -5.1 to 5.6 watts).
- Negligible mean decrease in MPI of -0.0 (95% CI: 0.0 to 0.0).

SAFETY RESULTS:

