9.5.1.2.5 Vital Signs

Vital signs (resting blood pressure and heart rate) were assessed at less than 1 hour prior to the first dose of study drug, 2 hours \pm 30 minutes after the first dose of study drug, immediately after self-limited 6-minute walk, 4 hours \pm 30 minutes after the first dose of study drug, and at Week 26.

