9.7.1.5.4 Vital Signs

Change from baseline (last vital sign value before the first dose of study drug at Visit 1) to each scheduled assessment was summarized descriptively by treatment group for each vital sign variable. Vital signs that were potentially clinically significant were identified according to prespecified criteria (listed in the SAP) and summarized descriptively by treatment group.

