summarized in [Table 42](#). There were no TEAEs for blood pressure or heart rate associated with these changes. Vital sign results for individual subjects are presented in [Listing 16.2.8.1](#).

Table 42: Potentially Clinically Significant Vital Sign Changes on Day 1 (Safety Population)

Vital Sign Time Point	Udenafil (N=200)	Placebo (N=200)
Low systolic blood pressure, n (%) with postdose value ≤ 80 mmHg and decreased ≥ 20 mmHg from value before dosing		
Pre-6MWT ^a	0	0
Post-6MWT ^a	0	0
≥ 1 event at either time point	0	0
High systolic blood pressure, n (%) with postdose value ≥ 140 mmHg and increased ≥ 20 mmHg from value before dosing		
Pre-6MWT ^a	0	0
Post-6MWT ^a	11 (5.5)	8 (4.0)
≥ 1 event at either time point	11 (5.5)	8 (4.0)
Low diastolic blood pressure, n (%) with postdose value ≤ 50 mmHg and decreased ≥ 15 mmHg from value before dosing		
Pre-6MWT ^a	2 (1.0)	2 (1.0)
Post-6MWT ^a	2 (1.0)	3 (1.5)
≥ 1 event at either time point	4 (2.0)	4 (2.0)
High diastolic blood pressure, n (%) with postdose value ≥ 100 mmHg and increased ≥ 15 mmHg from value before dosing		
Pre-6MWT ^a	0	1 (0.5)
Post-6MWT ^a	1 (0.5)	0
≥ 1 event at either time point	1 (0.5)	1 (0.5)
Low heart rate, n (%) with postdose value ≤ 45 bpm and decreased ≥ 15 bpm from value before dosing		
Pre-6MWT ^a	0	0
Post-6MWT ^a	1 (0.5)	0
≥ 1 event at either time point	1 (0.5)	0
High heart rate, n (%) with postdose value ≥ 130 bpm and increased ≥ 15 bpm from value before dosing		
Pre-6MWT ^a	0	0
Post-6MWT ^a	5 (2.5)	4 (2.0)
≥ 1 event at either time point	5 (2.5)	4 (2.0)

6MWT=6-minute walk test

a Approximately 2 hours after first drug administration.

Source: [Table 14.3.24](#)

Program: [T_14_3_24.sas](#)

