12.6 Safety Conclusions

A notably larger percentage (≥ 5 percentage points) of udenafil-treated than placebo-treated subjects reported at least 1 TEAE (79.0% versus 67.5%) and at least 1 drug-related TEAE (66.0% versus 42.5%). The incidence of TEAEs of Grade ≥ 3 , serious TEAEs, drug-related serious TEAEs, and TEAEs resulting in temporary or permanent discontinuation of study drug was similar between treatment groups.

A notably greater percentage (≥ 5 percentage points) of subjects in the udenafil group as compared to the placebo group reported headache (39.0% versus 25.5%), flushing (14.5% versus 6.0%), epistaxis (10.0% versus 3.0%), nausea (9.5% versus 4.5%), and erection increased (6.3% of males versus 0.8% of males).

There were no clinically important differences in the TEAE profile among subgroups defined by gender (female, male), race (Caucasian/White, non-Caucasian/White), ethnicity (Hispanic or Latino/Latina, not Hispanic or Latino/Latina), age (tertiles at baseline), and weight (tertiles at baseline).

Severe TEAEs were reported for 10 (5.0%) udenafil-treated subjects and 6 (3.0%) placebo-treated subjects; no life-threatening TEAEs were reported in either treatment group. Dizziness was the only severe TEAE reported by > 1 subject (2 placebo subjects).

No subject died during the study. At least 1 serious TEAE was reported by 14 (7.0%) subjects in the udenafil group and 10 (5.0%) subjects in the placebo group. No individual serious TEAE was reported by > 2 subjects in either treatment group. Hospitalization was reported for 23 subjects (14 udenafil, 9 placebo) during the study. No transplants were reported.

At least 1 TEAE leading to temporary or permanent discontinuation of study drug was reported by 18 (9.0%) subjects in the udenafil group and 13 (6.5%) subjects in the placebo group. Headache was the only TEAE leading to temporary or permanent discontinuation of study drug reported by > 2 subjects in either treatment group (3 subjects each in the udenafil and placebo groups).

There were no clinically important treatment group differences for clinical laboratory findings and vital signs.

Overall, udenafil was safe and well tolerated in this study.

13 Discussion and Overall Conclusions

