6.5.4 Vital Signs

Change from baseline (last value before dosing at Visit 1) to each scheduled assessment will be summarized descriptively by treatment group for each vital sign variable.

Vital signs that are potentially clinically significant will be identified with the criteria in Table 2 and summarized descriptively by treatment group. Baseline will be defined as the last vital sign value obtained before the first dose of study drug.

Table 2 Criteria for Potentially Clinically Significant Vital Signs

Vital Sign	Criterion	Definition of Potentially Clinically Significant Value
Systolic blood pressure	Low	Value \leq 80 mmHg and decreased \geq 20 mmHg from value before dosing
	High	Value \geq 140 mmHg and increased \geq 20 mmHg from value before dosing
Diastolic blood pressure	Low	Value \leq 50 mmHg and decreased \geq 15 mmHg from value before dosing
	High	Value \geq 100 mmHg and increased \geq 15 mmHg from value before dosing
Pulse	Low	Value \leq 45 bpm and decreased \geq 15 bpm from value before dosing
	High	Value \geq 130 mmHg and increased \geq 15 mmHg from value before dosing

bpm = beats per minute

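### Potentially clinically significant vital signs are counted only around the Day 1 walk, although the SAP sets no such limit and the report does not record the restriction

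*Protocol*

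**What the plan says.** SAP 6.5.4 has two parts. Change from the last pre-dose value "to each scheduled assessment will be summarized descriptively by treatment group for each vital sign variable". Then: "Vital signs that are potentially clinically significant will be identified with the criteria in Table 2 and summarized descriptively by treatment group". SAP Table 2 sets the thresholds; for low diastolic pressure the value must be 50 mmHg or less and at least 15 mmHg below the pre-dose value. Neither the sentence nor the table names a visit.

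Report section 9.7.1.5.4 repeats the rule, with values identified "according to prespecified criteria (listed in the SAP) and summarized descriptively by treatment group", again without a time limit. Section 9.5.1.2.5 lists readings before the first dose, at 2 hours, after the walk and at 4 hours "30 minutes after the first dose of study drug, and at Week 26". The SAP schedule also had resting blood pressure and heart rate at Weeks 2 and 13, until protocol version 3 removed them.

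In section 12.5 the results sentence covers only Day 1: percentages "pre-6-minute walk and post-6-minute walk on Day 1 were small and similar between treatment groups". Table 42 has a pre-walk row, a post-walk row and an either-time row per criterion, footnoted as about 2 hours after the first dose. Section 12.6 concludes: "There were no clinically important treatment group differences for clinical laboratory findings and vital signs".

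**The concern.** A threshold summary shows what mean changes cannot: how many individuals had a large fall to a low value. For a vasodilator taken twice daily for 26 weeks, readings around a single first dose do not show this under continued dosing. The weeks without threshold counts include the two at which Table 41 shows a greater mean diastolic fall on udenafil. A planned safety summary is therefore shown for part of its range, and the reader is not told that it was narrowed or why.

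**Working it through.** **1. Coverage of the planned summary**

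| Post-dose reading | In schedule | Mean change in Table 41 | Threshold counts in Table 42 |
|---|---|---|---|
| 2 hours, before walk | yes | no | yes |
| After walk | yes | no | yes |
| 4 hours | yes | no | no |
| Week 2 | until version 3 | yes | no |
| Week 13 | until version 3 | yes | no |
| Week 26 | yes | yes | no |

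Table 42 covers 2 of 6 readings under the SAP schedule, and 2 of 4 after version 3.

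**2. Is the restriction disclosed?** Section 9.8.2.2 adapts by-visit analyses to the loss of the Week 2 and Week 13 visits. That cannot explain leaving out the 4-hour reading or Week 26. Nothing else in 9.8.2 concerns vital-sign thresholds. Section 9.8.2.3 does record a comparable change for laboratory values, where the toxicity-grade criteria were replaced by shifts above normal.

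**3. Reproducing the diastolic results.** Table 41 uses a one-way analysis of variance on treatment group, which for two groups equals the pooled t-test: difference d, SE = s_p × √(1/n₁ + 1/n₂), where s_p² = [(n₁-1)s₁² + (n₂-1)s₂²]/(n₁+n₂-2). Inputs are the Table 41 changes, as mean (SD; n).

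| Visit | Udenafil | Placebo | d (mmHg) | SE | 95% CI | p | Stated p |
|---|---|---|---|---|---|---|---|
| Week 2 | -4.34 (12.113; 154) | -1.46 (12.398; 154) | -2.88 | 1.40 | -5.63 to -0.13 | 0.0401 | 0.040 |
| Week 13 | -3.75 (11.374; 131) | -1.95 (12.695; 143) | -1.80 | 1.46 | -4.68 to 1.08 | 0.219 | 0.220 |
| Week 26 | -3.01 (9.644; 189) | 0.05 (10.696; 190) | -3.06 | 1.05 | -5.12 to -1.00 | 0.0037 | 0.004 |

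The report's figures reproduce. In Table 42, low diastolic pressure at either Day 1 time is 4/200 = 2.0% in each group.

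**4. Could the later counts differ from Day 1? (illustration only)** The actual counts need the individual values in Listing 16.2.8.1. Assume baseline and follow-up diastolic pressure are bivariate normal, with Table 41 means and SDs, and a follow-up SD s_f of 0.9 to 1.1 times the baseline SD s_b. Neither assumption is in the documents. The correlation is then ρ = (s_b² + s_f² - s_d²)/(2 s_b s_f), where s_d is the SD of change. Simulating the probability of a value of 50 or less with a fall of 15 or more gives:

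| Visit | Udenafil | Placebo | Expected subjects |
|---|---|---|---|
| Week 2 | 3.5 to 5.8% | 1.6 to 3.3% | 5.4 to 8.9 vs 2.5 to 5.0 |
| Week 13 | 2.7 to 4.7% | 2.0 to 3.7% | 3.5 to 6.2 vs 2.8 to 5.3 |
| Week 26 | 1.4 to 2.9% | 0.7 to 1.7% | 2.7 to 5.6 vs 1.3 to 3.3 |

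The gap between groups follows mechanically from the mean shift and amounts to a few subjects, least at Week 13. The table shows only that the 4 versus 4 on Day 1 need not carry over.

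**The case against.** The strongest reply is that the report does not hide the later visits. Section 12.5 opens with Table 41 and says in plain terms that diastolic pressure fell significantly more on udenafil at Weeks 2 and 26. This stands. A reader might add the systolic counts (309 + 274 + 379 = 962 subject-visits) and call them omitted. They are in Table 41 as mean changes; only their threshold counts are missing. A reader might also infer that the 12.6 conclusion rests on Day 1 alone. Section 12.6 cites no table, so it may rest on Tables 41 and 42 together.

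Second, Table 37 gives a subject-level view over the treatment-emergent period: 18 (9.0%) versus 19 (9.5%) subjects with an event from the prespecified hypotension, dizziness and syncope cluster, syncope in 1 versus 3, and no hypotension row. This is real reassurance, but a reading that crosses a threshold need not be reported as an adverse event, so it does not replace the planned summary.

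Third, the SAP threshold sentence names no visits, and the phrase about each scheduled assessment belongs to the sentence on mean change. That is so. But a rule without a time limit, in a plan with visits to Week 26, does not read as a Day 1 rule. The FUEL Extension synopsis, whose list ends "ii) after the 6-minute walk, and iii) at any time after dosing", is another study and serves only as precedent.

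Fourth, Table 14.3.24, the source of Table 42, has no Day 1 limit in its title and was not available. It may already hold the later visits, in which case only their presentation is missing.

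Finally, the higher mean udenafil concentration at Week 26 (259.19 versus 174.99 ng/mL on Day 1) adds little. That sample was taken 2 hours after dosing, and section 9.5.1.2.5 does not time the Week 26 blood pressure relative to a dose.

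**Conclusion.** The point holds as a reporting gap. The SAP criteria carry no Day 1 limit, section 12.5 and Table 42 apply them only to the two readings around the first-dose walk, and section 9.8.2 does not say so. The 4-hour reading and Weeks 2, 13 and 26 have no threshold counts in the report text, and the 4-hour reading has no summary in Table 41 either.

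The gap matters because a mean diastolic effect of about 3 mmHg was seen at Weeks 2 and 26; Week 13 points the same way but is compatible with no difference. The documents do not show an excess of low readings on udenafil at later visits, and a reader should not infer one from the mean differences or from the illustration, which rests on assumed normality and an assumed follow-up SD. Nor do they show that the vital-sign conclusion is wrong. They show that one planned piece of evidence for it is not on the page. The point deserves correction but does not overturn the safety conclusion.

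**What to change.** Add rows to Table 42, and to Table 14.3.24 if they are absent there, for the 4-hour reading, Weeks 2, 13 and 26, and any time after dosing, for every SAP Table 2 criterion. Use the subjects assessed at each visit as denominators, not 200 throughout. Record in section 9.8.2 that the reported summary was limited to the Day 1 walk readings, with the reason. Restate the vital-sign sentence in section 12.6 in light of Tables 37, 41 and the extended Table 42.

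The cost is one table rerun on data already collected and listed in Listing 16.2.8.1. The drawback is fewer subjects at Weeks 2 and 13 (131 to 155 per group, against 189 and 190 at Week 26), because collection stopped mid-study. The any-time row will also mix subjects with different numbers of readings, so it should be read beside the by-visit rows.
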